10.4 APPENDIX 4: CONTRACEPTIVE GUIDANCE AND COLLECTION OF PREGNANCY INFORMATION

DEFINITIONS:

Woman of childbearing potential (WOCBP)

A woman is considered fertile following menarche and until becoming post-menopausal unless permanently sterile (see below).

Women in the following categories are not considered WOCBP

1. Premenarchal
2. Premenopausal female with 1 of the following:
 - Documented hysterectomy
 - Documented bilateral salpingectomy
 - Documented bilateral oophorectomy

Note: Documentation can come from the site personnel's: review of the participant's medical records, medical examination, or medical history interview.

3. Postmenopausal female
 - A postmenopausal state is defined as no menses for 12 months without an alternative medical cause. A high follicle stimulating hormone (FSH) level in the postmenopausal range may be used to confirm a postmenopausal state in women not using hormonal contraception or hormonal replacement therapy (HRT). However, in the absence of 12 months of amenorrhea, a single FSH measurement is insufficient.
 - Females on HRT and whose menopausal status is in doubt will be required to use one of the non-estrogen hormonal highly effective contraception methods if they wish to continue their HRT during the study. Otherwise, they must discontinue HRT to allow confirmation of postmenopausal status before study enrollment.

CONTRACEPTION GUIDANCE

Female participants

Female participants of childbearing potential are eligible to participate if they agree to use a highly effective method of contraception consistently and correctly as described in [Table 10](#) during the treatment period and for at least 5 weeks after the last dose of study treatment.

In addition, WOCBP must refrain from donating ova for the duration of the study and at least 5 weeks after last dose of study treatment.

Table 10 - Highly effective contraceptive methods

Highly effective contraceptive methods that are user dependent^a

Failure rate of <1% per year when used consistently and correctly.

Combined (estrogen and progestogen containing) hormonal contraception associated with inhibition of ovulation

- Oral^b
 - Intravaginal
 - Transdermal
-

Progestogen only hormonal contraception associated with inhibition of ovulation

- Oral^b
 - Injectable
-

Highly effective methods that are user independent^a

- Implantable progestogen only hormonal contraception associated with inhibition of ovulation
 - Intrauterine device (IUD)
 - Intrauterine hormone-releasing system (IUS)
 - Bilateral tubal occlusion
-

Vasectomized partner

A vasectomized partner is a highly effective contraception method provided that the partner is the sole male sexual partner of the WOCBP and the absence of sperm has been confirmed. If not, an additional highly effective method of contraception should be used.

Sexual abstinence

Sexual abstinence is considered a highly effective method only if defined as refraining from heterosexual intercourse during the entire period of risk associated with the study intervention. The reliability of sexual abstinence needs to be evaluated in relation to the duration of the study and the preferred and usual lifestyle of the participant.

NOTES:

- ^a Typical use failure rates may differ from those when used consistently and correctly. Use should be consistent with local regulations regarding the use of contraceptive methods for participants participating in clinical studies.
- ^b Pharmacokinetic drug interaction potential of oral hormonal contraception with the study treatment is low, but still unknown. Therefore, if the oral contraceptive cannot be replaced by another highly effective method of contraception, with a different route of administration, the hormonal contraception method must be supplemented with a male condom (for partner) during the treatment period and for at least 5 weeks after the last dose of study treatment..

PREGNANCY TESTING:

- WOCBP should only be included after a confirmed menstrual period and a negative highly sensitive serum pregnancy test.
- Additional pregnancy testing should be performed as displayed in the SoA in [Section 1.3](#) and as required locally.
- Pregnancy testing will be performed whenever a menstrual cycle is missed or when pregnancy is otherwise suspected

COLLECTION OF PREGNANCY INFORMATION:

[figure not shown]
Male participants with partners who become pregnant

- The Investigator will attempt to collect pregnancy information on any male participant's female partner who becomes pregnant while the male participant is in this study. This applies only to male participants who receive IMP.
- After obtaining the necessary signed informed consent from the pregnant female partner directly, the Investigator will record pregnancy information on the appropriate form and submit it to the Sponsor within 24 hours of learning of the partner's pregnancy. The female partner will also be followed to determine the outcome of the pregnancy. Information on the status of the mother and child will be forwarded to the Sponsor. Generally, the follow-up will be for at least one year following the estimated delivery date. Any termination of the pregnancy will be reported regardless of fetal status (presence or absence of anomalies) or indication for the procedure.

Female participants who become pregnant

[figure not shown]
- The Investigator will collect pregnancy information on any female participant who becomes pregnant while participating in this study. Information will be recorded on the appropriate form and submitted to the Sponsor within 24 hours of learning of a participant's pregnancy. The participant will be followed to determine the outcome of the pregnancy. The Investigator will collect follow-up information on the participant and the neonate and the information will be forwarded to the Sponsor. Generally, follow-up will be for at least one year beyond the estimated delivery date. Any termination of pregnancy will be reported, regardless of fetal status (presence or absence of anomalies) or indication for the procedure.
- Any pregnancy complication or elective termination of a pregnancy will be reported as an AE or SAE. A spontaneous abortion is always considered to be an SAE and will be reported as such. Any post-study pregnancy related SAE considered reasonably related to the study intervention by the Investigator will be reported to the Sponsor as described in [Section 8.3.4](#). While the Investigator is not obligated to actively seek this information in former study participants, he or she may learn of an SAE through spontaneous reporting.
- Any female participant who becomes pregnant while participating in the study will discontinue study intervention

10.5 APPENDIX 5: LIVER AND OTHER SAFETY: SUGGESTED ACTIONS AND FOLLOW-UP ASSESSMENTS

Neutropenia is to be recorded as an AE only if at least 1 of the criteria listed in the general guidelines for reporting adverse events in Appendix 3 (Section 10.3) is met.

THROMBOCYTOPENIA

[figure not shown]

Note:

The procedures above flowchart are to be discussed with the patient only in case described in the the event occurs. If applicable (according to local regulations), an additional consent (e.g., for HIV testing) will only be obtained in the case the event actually occurs.

Thrombocytopenia is to be recorded as an AE only if at least 1 of the criteria listed in the general guidelines for reporting adverse events in Appendix 3 ([Section 10.3](#)) is met.

INCREASE IN ALT

[figure not shown]

*If unable to retest in 72 hours, use original lab results to decide on further reporting/monitoring/discontinuation.

Note:

- “Baseline” refers to ALT sampled at baseline visit; or if baseline value unavailable, to the latest ALT sampled before the baseline visit. The algorithm does not apply to the instances of increase in ALT during screening.
- See Section X for guidance on safety reporting.
- Normalization is defined as \leq ULN or baseline value, if baseline value is $>$ ULN.

INCREASE IN SERUM CREATININE

[figure not shown]

If any of the above conditions are met, the Investigator should take corrective measures to resolve and schedule an interim visit to evaluate the serum creatinine/GFR and the patient's clinical status

1 week from the institution of corrective measures. Patients with a suspected renal event (reduction of eGFR) should have a repeat assessment of renal function 30 to 45 days following the onset of the event to confirm it is sustained. If acute renal failure is suspected, further clinical evaluation should be performed as per local standard of care, including confirmation of renal laboratory parameters, and consideration should be given to a nephrology referral.

Increase in serum creatinine is to be recorded as an AE only if at least 1 of the criteria listed in the general guidelines for reporting adverse events in Appendix 3 ([Section 10.3](#)) is met.

INCREASE IN CPK SUSPECTED TO BE OF NON-CARDIAC ORIGIN AND NOT RELATED TO INTENSIVE PHYSICAL ACTIVITY

Increase in CPK is to be recorded as an AE only if at least 1 of the criteria in the general guidelines for reporting adverse events in Appendix 3 ([Section 10.3](#)) is met.

10.6 APPENDIX 6: MONITORING AND MANAGEMENT OF PARTICIPANTS WITH INCREASED LIPASE AND/OR AMYLASE, OR CALCITONIN

10.6.1 Monitoring of participants with increased lipase and/or amylase >2 ULN

GLP-1 RAs stimulate pancreatic beta-cell and suppress alpha-cell function. Some cases of acute pancreatitis have been reported with marketed GLP-1 RAs. Therefore participants enrolled in this study should be closely monitored for any suspected pancreatitis, eg, with symptoms and/or signs of acute abdominal distress or abnormal levels of pancreatic enzymes. Serum amylase and lipase concentrations are monitored routinely at Screening, Baseline and periodically during the study treatment period.

In the presence of clinical signs and/or symptoms evocative of pancreatitis, eg, persistent abdominal pain, which can radiate to the back, often with characteristic positional features, with possible occurrence of nausea, vomiting, fever and leucocytosis, further measurement of amylase and lipase should be performed. The clinical signs and/or symptoms should be documented in the source data.

10.6.2 Elevation of amylase and/or lipase >2 x ULN without clinical signs and/or symptoms

In any case where amylase and/or lipase are >2 x ULN, a retest (centrally assessed as far as possible) must be performed as follows:

- If value(s) is/are >2 to 3 x ULN: retest within 7 days,
- If value(s) is/are >3 x ULN: retest within 48 hours,
- If the value(s) remain(s) >2 x ULN upon retesting: amylase and/or lipase levels should be retested weekly until values are <2 x ULN.

In case a retest is >2 x ULN a gastroenterological evaluation and imaging (ultrasound and/or computed tomography [CT] or magnetic resonance imaging [MRI] with contrast, as appropriate) must be performed. The absence of clinical signs and/or symptoms should be documented in the source documents (if clinical signs and/or symptoms develop, please see [Section 10.6.3](#) below).

Best clinical judgment is to be used when interpreting elevated serum amylase and lipase levels in asymptomatic participants. Temporary discontinuation of the IMP may be considered in these cases if deemed necessary by the Investigator.

10.6.3 Elevation of amylase and/or lipase >2 x ULN with clinical signs and/or symptoms.

In the presence of clinical signs and/or symptoms evocative of pancreatitis (as described above) associated with elevated amylase and/or lipase, treatment with the IMP should be promptly and at least temporarily discontinued pending further clinical evaluation and diagnosis confirmation. Clinical signs and/or symptoms are to be documented in the source data. A laboratory determination of amylase and lipase must be obtained at the time of the event and again within 48 hours or earlier as clinically indicated. If the value(s) remain(s) >2 x ULN, then amylase and/or

lipase levels should be retested as described in [Section 10.6.2](#) above, or more often if clinically indicated.

A gastroenterologic evaluation and imaging (ultrasound and/or CT or MRI with contrast, as appropriate) must be performed as clinically indicated and as per clinical practice and local guidelines. If a diagnosis of pancreatitis is confirmed, IMP should not be restarted and should be permanently discontinued. In both cases as described above under (1) and (2), all laboratory or clinical documentations are to be collected. If the retest confirms lipase and/or amylase values are >2 ULN, the event must be reported in the e-CRF on the AE form and the specific complementary forms, using the appropriate verbatim: eg, “increased amylase and/or lipase” in case of isolated enzyme elevation, “suspected pancreatitis” in the presence of clinical signs evocative of pancreatitis if the diagnosis is suspected but cannot be confirmed or excluded, and “pancreatitis” if the diagnosis has been confirmed.

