7.1.1 Permanent discontinuation of study intervention

Permanent intervention discontinuation is any intervention discontinuation associated with the definitive decision from the Investigator not to re-expose the participant to the IMP at any time during the study, or from the participant not to be re-exposed to the IMP whatever the reason.

The participants may withdraw from treatment with IMP if they decide to do so, at any time and irrespective of the reason. Patients should discuss stopping study medication with the site before doing so in order that questions can be addressed, concomitant therapy can be adjusted if needed, and a follow-up assessment arranged. All efforts should be made to document the reasons for treatment discontinuation and this should be documented in the e-CRF.

A participant should withdraw from treatment with IMP in case of the following:

- Intercurrent condition that requires discontinuation of IMP including:
 - laboratory abnormalities (see decision tree and general guidance for the follow up of laboratory abnormalities in Appendix 5 [[Section 10.5](#)])
 - diagnosis of acute pancreatitis confirmed by gastroenterologic evaluation and imaging, unless a clear cause unrelated to IMP is confirmed and the participant has recovered from pancreatitis (see Appendix 6 [[Section 10.6](#)])
 - calcitonin value ≥ 50 pg/mL (see Appendix 6 [[Section 10.6](#)])
- If, in the Investigator's opinion, continuation with the administration of IMP would be detrimental to the participant's well-being

- Pregnancy (in female patients)
- Confirmed intolerance to the allocated dose of IMP
- Any code breaking requested by the Investigator
- At the specific request of the Sponsor

See the SoA ([Section 1.3](#)) for data to be collected at the time of intervention discontinuation and follow-up and for any further evaluations that need to be completed.

Any abnormal laboratory value or ECG parameter will be immediately rechecked for confirmation (as soon as possible, preferably within 24 hours) before making a decision of permanent discontinuation of the IMP for the concerned participant.

Handling of participants after permanent intervention discontinuation

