8.3 ADVERSE EVENTS AND SERIOUS ADVERSE EVENTS

Adverse event of special interest

An AESI is an AE (serious or nonserious) of scientific and medical concern specific to the Sponsor's product or program, for which ongoing monitoring and immediate notification by the Investigator to the Sponsor is required. Such events may require further investigation in order to characterize and understand them. Adverse events of special interest may be added, modified or removed during a study by protocol amendment.

- Pregnancy of a female subject entered in a study as well as pregnancy occurring in a female partner of a male subject entered in a study with IMP (see [Section 8.3.5](#));
- Symptomatic overdose (serious or nonserious) with IMP
 - An overdose (accidental or intentional) with the IMP is an event suspected by the Investigator or spontaneously notified by the participant and defined as at least twice the planned dose (e.g. two or more injections) if given within 3 days (72 hours).
 - Of note, asymptomatic overdose has to be reported as a standard AE.
- ALT ≥ 3 ULN (if baseline ALT <ULN) Or ALT ≥ 2 times the baseline value (if baseline ALT \geq ULN) (Please refer to related flowchart in Appendix 5 [[Section 10.5](#)])

Adverse events requiring specific monitoring

An AE requiring specific monitoring is a serious or non-serious AE of scientific and medical concern specific to the Sponsor's product or program, for which ongoing monitoring may be appropriate. Such events may require further investigation to characterize and understand them. These events should be reported on the AE page and additional information required on specific e-CRF page (where applicable) and will only qualify for expedited reporting when serious (fulfilling SAE criteria).

The AE requiring specific monitoring for this study are:

- Severe GI events
- Severe hypoglycemia (see [Section 8.2.5](#))
- Pancreatic events (including abnormal values of pancreatic enzymes [see Appendix 6, [Section 10.6](#)])
- Calcitonin increase >5.9 pmol/L (20 pg/mL) and thyroid C-cell neoplasm (see Appendix 6, [[Section 10.6](#)])
- Acute renal failure (see Appendix 7 [[Section 10.7](#)])
- Diabetic retinopathy complications (will be reviewed by an independent ophthalmologist expert, see Appendix 1 [[Section 10.1.4.4](#)]); a written report from professional eye care provider will be required
- Severe injection site reactions
- Severe allergic reactions

- Severe immune complex disease

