**Table 2 - Criteria for AESI and AERSM**

AE Grouping	Criteria
AESI	
Pregnancy	"Pregnancy" checked
Symptomatic Overdose	"Overdose" checked and symptomatic (AEOVSYMP) = "Yes"
ALT $\geq$ 3 ULN (if baseline ALT <ULN) Or ALT $\geq$ 2 times the baseline value (if baseline ALT $\geq$ ULN)	"ALT Increase" checked and Yes to the question "Is the event an AESI?" in eCRF form "Adverse Events"
AERSM	
Severe GI events	AE severity= "severe" using Gastrointestinal disorders CMQ
Severe hypoglycemia	Any hypoglycemia event which either required assistance (from hypoglycemia page) or missed answering 'Assistance Required' but with at least one of the 4 symptoms of one of the 4 symptoms (ie, coma, seizure, loss of consciousness, and confusion)
Pancreatic events	cases reported in pancreatic specific eCRF page or AE with category = "Pancreatic neoplasm" selected
Calcitonin and thyroid C-cell neoplasm	Using Calcitonin increase CMQ Using Medullary thyroid cancer CMQ
Acute renal failure	Using Acute renal failure Narrow CMQ
Diabetic retinopathy complications	AE category = "Diabetic Retinopathy"
Severe injection site reaction	Intensity = "Severe" + Using Injection site reaction_ CMQ
Severe allergic reactions	Intensity = "Severe" + CMQs for anaphylactic reaction, angioedema, severe cutaneous adverse reaction, anaphylactic/anaphylactoid shock conditions (under SMQ "Shock"), and hypersensitivity
Severe immune complex disease	Intensity = "Severe" using Immune complex disease CMQ

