### Pancreatic events

The Pancreatic events will be reviewed, assessed and/or adjudicated by CEC.

The following analysis will be provided for positively adjudicated events during the TEAE period:

- The number (%) of patients with at least one positively adjudicated pancreatitis by type: 1) acute pancreatitis, 2) acute on chronic pancreatitis, 3) chronic pancreatitis, 4) unknown pancreatitis;
- The number (%) of patients with at least one positively adjudicated pancreatic neoplasm by type: 1) malignant - confirmed, 2) Malignant - probable, 3) Benign.

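### Appendix 6 ties the pancreatitis reporting forms to an enzyme retest, Section 8.3 does not, and the SAP finds pancreatitis only through the pancreatic eCRF page

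*Protocol*

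**What the plan says.** **Protocol Section 10.6.3** deals with participants who have symptoms plus raised amylase or lipase. On timing it says: "A laboratory determination of amylase and lipase must be obtained at the time of the event and again within 48 hours". The reporting rule follows later in the section: "If the retest confirms lipase and/or amylase values are >2 ULN, the event must be reported in the e-CRF on the AE form". The same sentence extends the requirement to the pancreatic forms: "and the specific complementary forms, using the appropriate verbatim". It then lists three labels: isolated enzyme increase; suspected pancreatitis, used "if the diagnosis is suspected but cannot be confirmed or excluded"; and pancreatitis once the diagnosis is confirmed.

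**Protocol Section 7.1.1** bases the treatment-discontinuation criterion on a "diagnosis of acute pancreatitis confirmed by gastroenterologic evaluation and imaging". It sets no retest threshold.

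**Protocol Section 8.3** lists pancreatic events, with enzyme abnormalities included, among the AEs requiring specific monitoring, and points to Appendix 6. Its general reporting rule for that whole list is: "These events should be reported on the AE page and additional information required on specific e-CRF page (where applicable").

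**SAP Table 2** defines the pancreatic grouping as "cases reported in pancreatic specific eCRF page", or an AE whose category is pancreatic neoplasm.

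**SAP Section 2.3.5.1, Pancreatic events,** introduces its tables of pancreatitis and neoplasm by type with: "The following analysis will be provided for positively adjudicated events during the TEAE period".

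**The concern.** A retest condition makes sense for an isolated laboratory finding, because it screens out transient elevations. It fits poorly with clinical pancreatitis, which these documents allow to be diagnosed by evaluation and imaging. There, whether the forms are explicitly mandated would depend on how quickly the enzymes fall and when the second sample was drawn.

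The SAP compounds this, because its pancreatic grouping starts from the pancreatic page. If a site reports a pancreatitis on the AE form but does not open that page, the grouping has no second way to find the case.

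Section 10.6.1 notes that acute pancreatitis has been reported with marketed drugs of this class and asks for close monitoring. Case-finding for this event should therefore not hinge on one form whose trigger is unclear.

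**Working it through.** No arithmetic applies. The documents give neither a pancreatitis rate nor the share of cases with a low retest. The check is to follow a case through the text.

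**Step 1: scope of the reporting sentence.** It opens with the retest condition, and everything after it (AE form, complementary forms, three labels) hangs on that condition. The preceding sentence refers to cases (1) and (2), but nothing in the appendix carries those numbers. They are probably Sections 10.6.2 and 10.6.3. Appendix 6 gives no separate reporting rule for pancreatitis with a retest at or below 2 x ULN.

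**Step 2: can such a case exist under the protocol?** Yes. Sections 7.1.1 and 10.6.3 both attach consequences to a confirmed diagnosis without reference to the retest value.

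**Step 3: does Section 8.3 settle it?** In part. It asks for the AE page with no retest condition, so the AE form is covered. For the specific page it adds the qualifier about applicability. It does not say what makes the page applicable, and its pancreatic entry refers to Appendix 6, where the retest condition stands.

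**Step 4: what each case reaches.**

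| Case | Section 10.6.3 | Section 8.3 | SAP Table 2 pancreatic grouping |
|---|---|---|---|
| Any of the three labels, retest >2 x ULN | AE and complementary forms mandated | AE page; specific page where applicable | Included |
| Suspected or confirmed pancreatitis, retest at or below 2 x ULN, site opens the pancreatic page | Silent | Same | Included |
| Same, but site uses the AE form only | Silent | AE page satisfied; specific page open to interpretation | Not included |

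**Step 5: is there a back-up in the SAP?** Table 2 uses coded-term searches (CMQs) for calcitonin and thyroid, acute renal failure, injection-site, allergic and immune-complex events. Pancreatitis has none, and the neoplasm category does not capture it. Yet SAP Section 2.1.4.1 names pancreatitis itself as part of the pancreatic category. The summary of events sent for adjudication and the investigator-CEC concordance rate sit in Section 2.3.4.2, under secondary efficacy, with concordance given by cardiac event type. No equivalent check is stated for pancreatitis.

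**Step 6: which outputs are exposed?** The pancreatic grouping in the specific-monitoring tables is exposed directly. The adjudicated table is exposed only if referral to the CEC also depends on the pancreatic page, which the documents do not say. The general TEAE tables by SOC and PT are not exposed, because they use the AE form.

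**The case against.** The strongest reply is that this is a drafting ambiguity, not a route by which cases are lost. Much of that stands.

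- **The sentence is a sufficient trigger, not an exclusive one.** It says when the forms must be completed; it does not say that they are otherwise not needed. A reader might infer an *only if*, but the text does not contain it.
- **Other rules still capture the event.** Section 8.3 asks for the AE page and Section 8.3.1 collects all AEs and SAEs. A treatment-emergent pancreatitis on the AE form enters the TEAE tables, the serious tables if it qualifies, and the discontinuation tables if it led to permanent discontinuation. A reader might infer that true cases vanish from the safety report; they would not.
- **Missed adjudication is not shown.** Protocol Section 10.1.4.3 and SAP Section 2.3.5.1 send pancreatic events to the CEC with no enzyme condition. Neither document says that the pancreatic page is what triggers referral; CEC roles are left to a separate charter.
- **The applicability qualifier has an innocent reading.** It covers nine event types and may simply mean wherever a dedicated page exists.
- **No bias between arms follows.** The rule is the same in every arm of a blinded trial, and the safety analysis is descriptive. A reader might infer a hidden or reversed imbalance; nothing in the documents supports differential loss.

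Two things survive. The literal text of Section 10.6.3 places confirmed pancreatitis under a laboratory condition that Section 8.3 does not impose. And SAP Table 2, as written, would omit a pancreatitis recorded on the AE form alone.

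**Conclusion.** The point holds as an inconsistency in reporting instructions, combined with a SAP case definition that rests on one form. The omission from the pancreatic grouping follows directly from Table 2 for any pancreatitis on the AE form only. Non-referral to the CEC is a possibility that the documents neither establish nor exclude.

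The number of affected cases cannot be estimated. It would need the pancreatitis rate on treatment, the share with a retest at or below 2 x ULN, and the share of those for which the site does not open the page. None is given. The only observed figure, in Protocol Section 2.3, is no pancreatitis reported in the Phase 1 and 2 studies. Multiplying assumed rates by total study follow-up would also use too large a base, because the adjudicated table is limited to the period from first injection to 30 days after the last.

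The primary and secondary efficacy analyses are untouched. The point is worth acting on because this is a named class concern and the correction is small.

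**What to change.** These changes affect reporting and analysis only; no dosing, stopping or other clinical rule is altered.

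1. **Protocol Section 10.6.3:** state that suspected or confirmed pancreatitis is reported on the AE form and the pancreatic form whatever the retest shows. Keep the retest condition for isolated enzyme elevations. Align Section 8.3 with this, and replace the unnumbered (1) and (2) with section references.
2. **SAP Table 2, pancreatic events:** extend the criterion with: or any AE coded to a pancreatitis term. Name the search to be used.
3. **Reconciliation:** compare those AEs with the CEC referral list and refer any not yet sent. SAP Section 4 plans the lock about 4 to 6 weeks after the last patient's last visit, so this should run during the study and be completed before lock.

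If the protocol can no longer be amended, items 2 and 3 alone would still pick up cases recorded on the AE form.

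The cost is one sentence in Appendix 6 with its cross-references, one line in the SAP, and a few extra forms and adjudications, some of which will not be confirmed.
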